Appendix A: Laboratory assays: The following information has been added.

SAFETY LABORATORY TESTING: CLS South Africa

Cerebrospinal fluid (CSF) for meningitis testing

The recommended method for evaluation of meningitis will be through CSF analysis. The minimum acceptable volume for CSF should be 500 µl.

All CSF samples for suspected meningitis cases will be sent to CLS South Africa for CSF polymerase chain reaction (PCR) testing for selected common aetiological pathogens of meningitis as listed below.

- **CSF: PCR testing**

	TEST
Bacteria	Haemophilus influenzae
	Streptococcus pneumoniae
	Neisseria meningitidis
	Salmonella enterica
	Mycobacterium tuberculosis
Viruses	Adenovirus
	Cytomegalovirus
	Enterovirus
	Epstein Bar virus
	Herpes simplex virus 1 & 2
	HHV 6
	Rabies
Parasite	Mumps virus
	Plasmodium spp

The following additional tests are available at CLS South Africa and can be requested by the treating clinician if required.

- *CSF: Other possible PCR testing*

	TEST
Bacteria	Borrelia burgdorferi *
	Brucella spp. *
	Coxiella burnetii *
	Ehrlichia spp. *
	Leptospira spp. *
	Rickettsia spp. *
Viruses	Chikungunya *
	Crimean-Congo haemorrhagic fever virus *
	Dengue virus *
	Flavivirus genus *
	Hepatitis A virus *
	Hepatitis B virus *
	JC virus *
	Measles virus *
	Rift valley fever virus *
	Sindbis virus *
	Rubella virus *
	Varicella zoster virus *
	West Nile virus *
Parasite	Toxoplasmosis

* These tests are performed in a multiplex PCR.

An additional blood sample of approximately 5 ml whole blood may be taken at the discretion of the treating clinician to aid in the diagnosis of meningitis through serum PCR or serum serology. The following tests will be available at CLS South Africa, if not available locally.

- *Serum: PCR*

	TEST
Viruses	Cytomegalovirus
	Enterovirus
	Haemophilus Influenza
	Varicella
Parasite	Toxoplasmosis

- *Serum: Serology*

	TEST
Bacteria	Beta haemolytic streptococcus
	Mycoplasma pneumoniae
	Streptococcus pneumoniae
Viruses	CMV IgG & IgM
	Epstein-Barr virus
	HSV IgG
	HSV IgM
	Measles IgG/IgM
	Mumps IgG/IgM
	Rabies IgG/IgM
	VZV IgG/IgM
Parasites	Cryptococcus

Analysis of potential Immune-Mediated Diseases (pIMDs)

The medical and scientific judgement of the investigator is required in deciding whether other disorders not mentioned in the list of pIMDs have enough evidence of an autoimmune origin.

A volume of approximately 5 ml of whole blood will be required for testing. A list of potential serum autoimmune tests that can be performed at CLS South Africa is provided below.

- *Serum: Autoimmune tests*

TEST
Anti-insulin autoantibodies (IA2)*
Anti-glutamic acid decarboxylase autoantibodies (anti-GAD65)
Anti-Tyrosine phosphatase-like IA2 antibodies
Anti-islet cell antibodies
Anti-smooth muscle antibodies (ASMA)
Anti-liver-kidney microsomal antibodies (anti-LKM)
Anti-soluble liver antigens (anti-SLA)
Anti-mitochondrial antibodies (AMA)
Anti-nuclear antibodies (ANA)
Anti-double stranded DNA (anti-dsDNA)
Rheumatoid factor (RF)
Anti-Glomerular Basement Membrane antibodies (anti-GBM)
Anti-neutrophil cytoplasmic autoantibodies (ANCAs)
Anti-streptolysin O / Anti-DNAse
Serum C3, C4 complement
Anti-cyclic citrullinated peptide antibodies (anti-CCP)
Anti-skin basement membrane protein
IgA endomysial antibodies
Anticardiolipin (ELISA) IgM, IgG
Anti-beta 2 glycoprotein I
Anti-prothrombin

Measles/Rubella confirmatory testing

Confirmatory testing for measles and rubella may be required for suspected cases. A volume of approximately 5 ml of whole blood will be required for confirmatory serology to be sent to CLS South Africa.

Table 20: GSK Biologicals' laboratories

Laboratory	Address
GSK Biologicals Clinical Laboratory Sciences Global Vaccine Clinical Laboratory, Rixensart	Biospecimen Reception - B7/44 [name]
GSK Biologicals Global Vaccine Clinical Laboratory, North America - Laval	Biospecimen Reception - Clinical Serology [name]
GSK Biologicals Clinical Laboratory Sciences Global Vaccine Clinical Laboratory, Wavre-Nord Noir Epine	[name]

Table 21: Outsourced laboratories

Laboratory	Address
Focus Diagnostics, Inc.	[name]
CEVAC - University of Gent	[name]
NEOMED-LABS Inc	[name]

Template 43	Incidence of seizures by diagnostic certainty level and history of fever within 7 days (1-7) post vaccination overall doses (Diagnostic certainty 1-5), per study group (Exposed Set)	72
Template 44	Incidence of seizures by diagnostic certainty level and fever within 7 days (1-7) post vaccination overall doses (Diagnostic certainty 1-5), per study group (Exposed Set)	73

Template 45	Incidence of concomitant medication administered during the <30-day (Days 1-30) post-vaccination period by dose and overall, per study group (Exposed Set)	74
Template 46	Number (%) of subjects with serious adverse events including number of events reported during the study period (Exposed Set)	74
Template 47	Solicited and unsolicited symptoms, classified by MedDRA Primary System Organ Class and Preferred Term within the 42-day (Days 1-42) post-vaccination period including number of events - SAE excluded (Exposed Set).....	75
Template 48	Listing of dropouts due to AEs, SAEs and solicited symptoms (Exposed Set)	75

LIST OF ABBREVIATIONS

AE	Adverse event
ANOVA	Analysis of Variance
Anti-CS	Antibody to the Plasmodium falciparum circumsporozoite (CS) repeat domain
Anti-HBs	Antibody to the hepatitis B surface antigen
Anti-Me	Anti-measles antibody
Anti-Ru	Anti-rubella antibody
Anti-YF	Anti-yellow fever antibody
AS01 _E	GSK's proprietary Adjuvant System containing MPL, QS-21 Stimulon [®] and liposome (25 µg MPL and 25 µg QS-21 Stimulon [®])
CI	Confidence interval
Coad	Co-administration
CS	Circumsporozoite protein of Plasmodium falciparum
eCRF	Electronic case report form
ED50	End point Dilution 50
EPI	Expanded Program on Immunization
ES	Exposed Set
EU/ml	ELISA unit per milliliter
GMC	Geometric mean antibody concentration
GMT	Geometric mean antibody titre
GSK	GlaxoSmithKline
ICH	International Conference on Harmonization
IDMC	Independent Data Monitoring Committee
IU/ml	International units per milliliter
LL	Lower Limit of the confidence interval
MedDRA	Medical Dictionary for Regulatory Activities
N.A.	Not Applicable
PD	Protocol Deviation

[figure not shown]
pIMD	Potential immune-mediated disease
PPS	Per Protocol Set
RCD	Reverse cumulative distribution
RTS,S	Particulate antigen, containing both RTS and S (hepatitis B surface antigen) proteins
RTS,S/AS01 _E	GSK Biologicals' candidate Plasmodium falciparum malaria vaccine adjuvanted with GSK Biologicals' proprietary Adjuvant System AS01 _E
SAE	Serious adverse event
SAP	Statistical Analysis Plan
SD	Standard Deviation
SR	Study Report
TFL	Tables Figures and Listings
TOC	Table of Content
UL	Upper Limit of the confidence interval
YF	Yellow fever

1. DOCUMENT HISTORY

Date	Description	Protocol Version
09-APR-2018	Final version	Amendment 1 Final – 09-AUG-2016

2. STUDY DESIGN

Figure 1 Study design

- Experimental design: Phase IIIB, open, randomized, controlled, multi-centric study with three parallel groups.
- Duration of the study: Approximately 33 months per participant in the Coad or the RTS,S group and 36 months in the Control group.
 - Epoch 001: Primary starting at Visit 1 (Screening) and ending at Visit 15 (Month 36).
- Study groups: 3 study groups are defined for the study (Coad group, RTS,S group and Control group). A description of the vaccination, blood sample and visit schedule is provided for each of the study groups in [Figure 1](#).

Table 1 Study groups and epochs foreseen in the study

Study groups	Number of subjects	Age (Min)	Epoch 001
Coad group	233	6 months*	X
RTS,S group	233	6 months*	X
Control group	233	6 months*	X

* For clarity this corresponds from the day the child becomes 6 months of age until the day before the child achieves 7 months of age.

Table 2 Study groups and treatment foreseen in the study

Treatment name	Vaccine/Product name	Study groups		
		Coad group	RTS,S group	Control group
RTS,S/AS01 _E	RTS,S	X	X	X
	AS01E	X	X	X
Yellow fever	WHO prequalified Yellow Fever	X	X	X
Measles and Rubella	MR-VAC	X	X	X
Vitamin A	Vitamin A	X	X	X

MR-VAC: Live attenuated measles virus and rubella virus vaccine (Serum Institute of India)

- Treatment allocation: randomized in a 1:1:1 ratio to each study group.
- Blinding: open

Table 3 Blinding of study epoch

Study Epoch	Blinding
Epoch 001	open

- Type of study: self-contained.
- Data collection: Electronic Case Report Form (eCRF).
- Safety monitoring: description of safety monitoring is available in [Table 5](#)
- Immunogenicity monitoring:

Table 4 Immunological read-outs

Blood sampling timepoint		study group	No. subjects	Component	Components priority rank
Type of contact and timepoint	Sampling timepoint				
Visit 2	Day 0	Coad group and RTS,S group	466	anti-CS	1
		Coad group and RTS,S group	466	anti-HBs	2
		Coad group and Control group	466	anti-catalase	3
Visit 4	Month 3	Coad group and Control group	466	anti-Me	1
		Coad group and Control group	466	anti-Ru	2
Visit 5	Month 4	Coad group and RTS,S group	466	anti-CS	1
		Coad group and RTS,S group	466	anti-HBs	5
		Coad group and Control group	466	anti-catalase	6
		Coad group and Control group	466	anti-Me	2
		Coad group and Control group	466	anti-Ru	3
		Coad group and Control group	466	anti-YF	4

Table 5 Reporting periods for adverse events and serious adverse events

Visit	1	2	3	4	5	6	7	8	9	10	11	12	13	14	15
Children age (Months)		6	7.5	9	10	10.5	11.5	12.5	13.5	27	28	30	31	39	42
Study Month		M0	M1.5	M3	M4	M4.5	M5.5	M6.5	M7.5	M21	M22	M24	M25	M33	M36
	D-28 to -1	D0 D6 D29	M1.5 M1.5 M1.5 +6d +29d	M3 M3 M3 +13d +41d											
Solicited local and general AEs		X ^a X ^a	X ^a X ^a	X ^a											
Unsolicited AEs		X ^b X ^b X ^b	X ^b X ^b X ^b	X ^b X ^b X ^b	X ^b	X ^{b,c}	X ^c X ^c X ^c			X ^d X ^d	X ^e X ^e				
SAEs related to study participation or concurrent GSK medication/vaccine															
SAEs (All, fatal, related to the investigational vaccine)															
AEs of specific interest**															

M: study month; d: day

** AEs of specific interest include seizure (occurring within 30 days post-vaccination for vaccine doses administered at 6 and 7.5 months of age [Visits 2 and 3] or 42 days post-vaccination for vaccine doses administered at 9 months of age [Visit 4]), meningitis and pIMDs.

a In the Control group, only solicited general AE will be collected. In the Coad and the RTS,S groups, solicited local and general AEs will be collected.

b Unsolicited AEs will be collected from Visit 2 until 42 days after Visit 4 for children in Coad, RTS,S and Control groups.

c Unsolicited AEs will be collected from Visit 6 until 30 days after Visit 8 only for children from the Control group.

d Unsolicited AEs will be collected over a 30-day follow-up period after vaccination only for children from the Coad and the RTS,S groups.

e Unsolicited AEs will be collected over a 30-day follow-up period after vaccination only for children from the Control group.

3. OBJECTIVES

3.1. Primary objective

- To demonstrate the non-inferiority of the antibody response to the CS antigen when RTS,S/AS01_E is co-administered with YF vaccine and a combined measles and rubella vaccine versus RTS,S/AS01_E administered alone.
 - *Criteria for non-inferiority: one month post Dose 3 of RTS,S/AS01_E, the upper limit (UL) of the 2-sided 95% confidence interval (CI) on the geometric mean titre (GMT) ratio (RTS,S group/Coad group) of the anti-CS, is below a limit of 2.*

Refer to Section 4.1 for the definition of the primary endpoints.

3.2. Secondary objectives

Immunogenicity

- To describe the antibody response to the CS antigen when RTS,S/AS01_E is administered at 6, 7.5 and 9 months of age in co-administration with YF vaccine and a combined measles and rubella vaccine versus RTS,S/AS01_E administered alone.
- To describe the antibody response to the hepatitis B surface (HBs) antigen when RTS,S/AS01_E is administered at 6, 7.5 and 9 months of age in co-administration with YF vaccine and a combined measles and rubella vaccine versus RTS,S/AS01_E administered alone.
- To demonstrate the non-inferiority of the antibody response to the measles vaccine antigen when YF vaccine and a combined measles and rubella vaccine are co-administered with RTS,S/AS01_E versus administration without RTS,S/AS01_E.
 - *Criteria for non-inferiority: one month post-vaccination with the combined measles and rubella vaccine, the UL of the 95% CI on the difference in seroconversion rates of the anti-measles antibody (anti-Me), is below 10% (Control group minus Coad group).*
- To describe the antibody response to the measles vaccine antigen when YF vaccine and a combined measles and rubella vaccine are co-administered with RTS,S/AS01_E versus administration without RTS,S/AS01_E.
- To demonstrate the non-inferiority of the antibody response to the rubella vaccine antigen when YF vaccine and a combined measles and rubella vaccine are co-administered with RTS,S/AS01_E versus administration without RTS,S/AS01_E.
 - *Criteria for non-inferiority: one month post-vaccination with the combined measles and rubella vaccine, the UL of the 95% CI on the difference in seroconversion rates of the anti-rubella antibody (anti-Ru), is below 10% (Control group minus Coad group).*

- To describe the antibody response to the rubella vaccine antigen when YF vaccine and a combined measles and rubella vaccine are co-administered with RTS,S/AS01_E versus administration without RTS,S/AS01_E.
- To demonstrate the non-inferiority of the antibody response to the YF vaccine antigen when YF vaccine and a combined measles and rubella vaccine are co-administered with RTS,S/AS01E versus administration without RTS,S/AS01E.
 - *Criteria for non-inferiority: one month post-vaccination with the YF vaccine, the UL of the 95% CI on the difference in seropositivity rates of the anti-yellow fever antibody (anti-YF), is below 10% (Control group minus Coad group).*
- To describe the antibody response to the YF vaccine antigen when YF vaccine and a combined measles and rubella vaccine are co-administered with RTS,S/AS01_E versus administration without RTS,S/AS01_E.

Safety

- Evaluation of the safety profile of RTS,S/AS01_E when administered at 6, 7.5 and 9 months of age in co-administration with YF vaccine and a combined measles and rubella vaccine versus RTS,S/AS01_E administered alone.

Refer to Section 4.2 for the definition of the secondary endpoints.

3.3. Tertiary objective

Immunogenicity

- To describe the antibody response to the human catalase after administration of a 3-dose course of RTS,S/AS01_E.

Refer to Section 4.3 for the definition of the tertiary endpoint.

4. ENDPOINTS

4.1. Primary endpoints

- Non-inferiority of the antibody response to the CS antigen (RTS,S group/Coad group):
 - Anti-CS antibody titres at one month post Dose 3 of RTS,S/AS01_E (Month 4).

4.2. Secondary endpoints

Immunogenicity

- Antibody response to the candidate vaccine RTS,S/AS01_E (RTS,S group and Coad group):
 - Anti-CS antibody titres and seropositivity (≥ 1.9 EU/ml) at Day 0 and at one month post Dose 3 of RTS,S/AS01_E (Month 4).
 - Anti-HBs antibody titres and seroprotection (≥ 10 mIU/ml) at Day 0 and at one month post Dose 3 of RTS,S/AS01_E (Month 4).
- Non-inferiority of the antibody response to the measles vaccine antigen in the combined measles and rubella vaccine (Control group minus Coad group):
 - Seroconversion for anti-Me at one month post-vaccination with the combined measles and rubella vaccine (Month 4). Seroconversion is defined as children with an anti-Me pre-vaccination titre below 150 mIU/ml and a post-vaccination titre ≥ 150 mIU/ml.
- Antibody response to the measles vaccine antigen in the combined measles and rubella vaccine (Control group and Coad group):
 - Anti-Me antibody titres and seropositivity (≥ 150 mIU/ml) pre-vaccination (Month 3) and one month post-vaccination with the combined measles and rubella vaccine (Month 4).
- Non-inferiority of the antibody response to the rubella vaccine antigen in the combined measles and rubella vaccine (Control group minus Coad group):
 - Seroconversion for anti-Ru at one month post-vaccination with the combined measles and rubella vaccine (Month 4). Seroconversion is defined as children with an anti-Ru pre-vaccination titre below 4 IU/ml and a post-vaccination titre ≥ 4 IU/ml.
- Antibody response to the rubella vaccine antigen in the combined measles and rubella vaccine (Control group and Coad group):
 - Anti-Ru antibody titres and seropositivity (≥ 4 IU/ml) pre-vaccination (Month 3) and one month post-vaccination with the combined measles and rubella vaccine (Month 4).
- Non-inferiority of the antibody response to the YF vaccine antigen (Control group minus Coad group):
 - Seropositivity (≥ 10 ED50) for anti-YF at one month post-vaccination with the YF vaccine (Month 4).
- Antibody response to the YF vaccine antigen (Control group and Coad group):
 - Anti-YF antibody titres and seropositivity (≥ 10 ED50) one month post-vaccination with the YF vaccine (Month 4).

Safety

- Solicited local and general AEs.
 - For the Coad and the RTS,S groups, the occurrence of solicited local and general AEs over a 7-day follow-up period (day of administration and 6 subsequent days) after administration of Vitamin A and study vaccines at 6 months of age (Visit 2).
 - For the Control group, the occurrence of solicited general AEs over a 7-day follow-up period (day of administration and 6 subsequent days) after administration of Vitamin A at 6 months of age (Visit 2).
 - For the Coad and the RTS,S groups, the occurrence of solicited local and general AEs over a 7-day follow-up period (day of vaccination and 6 subsequent days) after dose of study vaccines administered at 7.5 months of age (Visit 3).
 - For the Control group, the occurrence of solicited general AEs over a 7-day follow-up period (day of visit and 6 subsequent days) after Visit 3 (7.5 months of age).
 - For all groups, the occurrence of solicited general and local AEs over a 14-day follow-up period (day of vaccination and 13 subsequent days) after dose of study vaccines administered at 9 months of age (Visit 4).
- Unsolicited AEs.
 - For all groups, the occurrence of unsolicited AEs over a 30-day follow-up period (day of administration and 29 subsequent days) after administration of Vitamin A and study vaccines at 6 months of age (Visit 2).
 - For the Coad and the RTS,S groups, the occurrence of unsolicited AEs over a 30-day follow-up period (day of vaccination and 29 subsequent days) after dose of study vaccines administered at 7.5 months of age (Visit 3).
 - For the Control group, the occurrence of unsolicited AEs over a 30-day follow-up period (day of visit and 29 subsequent days) after Visit 3 (7.5 months of age).
 - For all groups, the occurrence of unsolicited AEs over a 42-day follow-up period (day of vaccination and 41 subsequent days) after dose of study vaccines administered at 9 months of age (Visit 4).
 - For the Coad and the RTS,S groups, the occurrence of unsolicited AEs over a 30-day follow-up period (day of vaccination and 29 subsequent days) after the booster dose of study vaccine administered at 27 months of age (Visit 10).
 - For the Control group, the occurrence of unsolicited AEs over a 30-day follow-up period (day of vaccination and 29 subsequent days) after dose of study vaccines administered at 10.5, 11.5, 12.5 and 30 months of age (Visit 6, 7, 8 and 12).

- SAEs: all, fatal and related SAEs.
 - The occurrence of SAEs occurring within 30 days (day of vaccination and 29 subsequent days) after each administration.
 - The occurrence of SAEs from Screening visit (Visit 1) until Month 4.5.
 - The occurrence of SAEs from Screening visit (Visit 1) until study end (Month 33 for Coad and RTS,S groups and Month 36 for the Control group).
 - The occurrence of pIMDs from Day 0 until Month 4.5.
 - The occurrence of pIMDs from Day 0 until study end (Month 33 for Coad and RTS,S groups and Month 36 for the Control group).
 - The occurrence of meningitis from Day 0 until Month 4.5.
 - The occurrence of meningitis from Day 0 until study end (Month 33 for Coad and RTS,S groups and Month 36 for the Control group).
 - The occurrence of seizure (occurring within 30 days post-vaccination for vaccine doses administered at 6 and 7.5 months of age [Visits 2 and 3] or 42 days post-vaccination for vaccine doses administered at 9 months of age [Visit 4]) from Day 0 until Month 4.5.
 - The occurrence of seizure occurring within 30 days post-vaccination for vaccine doses administered at 6, 7.5 and 27 months of age (Visits 2, 3 and 10 for Coad and RTS,S group) and at 10.5, 11.5, 12.5 and 30 months of age (Visits 6, 7, 8 and 12 for Control group) or 42 days post-vaccination for vaccine doses administered at 9 months of age (Visit 4 for all groups).
 - The occurrence of generalized convulsive seizure occurring within 7 days after vaccines administered at Visit 2 and 3 (Coad and RTS,S groups) and 14 days after vaccines administered at Visit 4 (all groups).

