^a Study personnel will visit the children on Days 1, 2, 3, 4, 5 and 6 after Vitamin A administration (Visit 2) and after Visit 3 to record solicited general and unsolicited AEs on diary cards.^b Study personnel will visit the children on Days 1, 2, 3, 4, 5, 6, 7, 8, 9, 10, 11, 12, and 13 after vaccination to record solicited and unsolicited AEs on diary cards.^c Collection of solicited local AE for the two injection sites.^d Seizures occurring within 30 days post-vaccination for vaccine doses administered at 6 and 7.5 months of age (Visits 2 and 3) or 42 days post-vaccination for vaccine doses administered at 9 months of age (Visit 4).

Note: The double-line border following Month 4.5 (Visit 6) indicates the analyses which will be performed on all data (i.e. data that are as clean as possible) obtained up to Month 4.5.

* If the investigator believes there is a reasonable reason to do so, screening procedures may only be repeated once.

† Confirmatory serology tests should be performed to identify cases of vaccine failure.

● is used to indicate a study procedure that requires documentation in the individual eCRF.

○ is used to indicate a study procedure that does not require documentation in the individual eCRF.

Table 7 Intervals between study visits (Amended: 09 August 2016)

Study visit	Timing of visit ^a	Allowed interval ^b
Visit 1 (Screening) ^c	1-28 days before Visit 2	-
Visit 2	6 months of age	Child should be 6 ^c months of age
Visit 3	7.5 months of age	Child should be 7 ^d or 8 ^e months of age but respecting a minimum of 4 weeks (28 days) since previous dose (Visit 2)
Visit 4	9 months of age	Child should be 9 ^f months of age but respecting a minimum of 4 weeks (28 days) since previous dose (Visit 3)
Visit 5	4 weeks after Visit 4	Minimum 4 weeks (28 days) - Maximum 6 weeks (42 days)
Visit 6	2 weeks after Visit 5	Minimum 2 weeks (14 days) - Maximum 3 weeks (21 days)
Visit 7	4 weeks after Visit 6	Minimum 4 weeks (28 days) - Maximum 6 weeks (42 days)
Visit 8	4 weeks after Visit 7	Minimum 4 weeks (28 days) - Maximum 6 weeks (42 days)
Visit 9	4 weeks after Visit 8	Minimum 4 weeks (28 days) - Maximum 6 weeks (42 days)
Visit 10	18 months after Visit 4	17 months (516 days) after Visit 4 – 19 months (577 days) after Visit 4
Visit 11	4 weeks after Visit 10	Minimum 4 weeks (28 days) - Maximum 6 weeks (42 days)
Visit 12	17.5 months after Visit 8	17 months (516 days) after Visit 8 – 19 months (577 days) after Visit 8

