The proportion of subjects reporting an AEs of specific interest (pIMDs, meningitis and seizures) from Day 0 to Month 4.5 and over the whole study duration (Day 0 to Month 33 for Coad and RTS,S groups and Month 36 for the Control group), classified by the MedDRA preferred term level will be tabulated with exact 95% CI.

For generalized convulsive seizures occurring within 7 days after vaccines administered at Visit 2 and 3 (Coad and RTS,S groups) and 14 days after vaccines administered at Visit 4 (all groups) an analysis will be performed based on the Brighton Collaborations guidelines [**Bonhoeffer**, 2004]. This includes descriptive tables of the time relationship of seizures to vaccination, the duration of seizures and the level of diagnostic certainty.

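### The seizure endpoints do not treat the Control group consistently after Visits 2 and 3: up to Month 4.5 Control has 102 or 42 scored days per child, depending on the reading

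*SAP*

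**What the plan says.** SAP 4.2 and protocol 10.2 carry the same three seizure endpoints.

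- **Up to Month 4.5:** seizures in the window "30 days post-vaccination for vaccine doses administered at 6 and 7.5 months of age [Visits 2 and 3", plus 42 days after the 9-month doses. No group is named, but the window depends on a vaccine dose.
- **Whole study:** 30 days after "vaccine doses administered at 6, 7.5 and 27 months of age (Visits 2, 3 and 10 for Coad and RTS,S group". Control's own 30-day windows follow the doses it receives "at 10.5, 11.5, 12.5 and 30 months of age (Visits 6, 7, 8 and 12 for Control group". Every group also has 42 days after Visit 4. Control is not listed for Visits 2 and 3.
- **Generalized convulsive seizure:** "within 7 days after vaccines administered at Visit 2 and 3 (Coad and RTS,S groups", plus 14 days after Visit 4 in every group.

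Control receives Vitamin A but no vaccine at Visit 2, and no product at Visit 3 (protocol section 3 and Table 12). Even so, protocol Table 6, which is Control's own schedule, marks recording of AEs of specific interest from Visit 2. Its footnote d reads "Seizures occurring within 30 days post-vaccination for vaccine doses administered at 6 and 7.5 months of age (Visits 2 and 3". Protocol 8.1.5.2 defines the reportable seizures by the same dose-based windows. Protocol 8.2.1 starts recording of AEs of specific interest at the first study vaccine, which for Control is literally Visit 4. The same section starts Control's general AE collection at Vitamin A.

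For other outcomes SAP 4.2 gives Control a window anchored on the visit: its unsolicited AEs, for example, are scored for 30 days from Visit 3, counting the visit day itself. SAP 6.5.1 tabulates "AEs of specific interest (pIMDs, meningitis and seizures) from Day 0 to Month 4.5 and over the whole study duration", with no restriction of visits by group.

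**The concern.** Protocol 1.3.1 lists febrile convulsion as an important identified risk of RTS,S/AS01E, with the increase seen within seven days of vaccination. At 6 and 7.5 months Control is the only randomized group without RTS,S. Its seizures in those weeks are the concurrent background for RTS,S doses 1 and 2. Two endpoints exclude that background, one does not say, and the recording rules point in both directions. Two competent programmers could produce different Control counts from the same data, and few events are expected.

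**Working it through.** **Inputs.** Windows come from SAP 4.2. I assume the counting convention given there for unsolicited AEs also applies to seizures (day of visit plus 29 days = 30 days; plus 41 days = 42 days). Visit intervals come from protocol Table 7, and 233 children per group from protocol 10.4. The plan gives no figure of its own to reproduce.

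**Step 1. Do the Visit 2, 3 and 4 windows fall inside the Month 4.5 period?** The Visit 3 window ends on Day 29 and Visit 4 is at least 28 days after Visit 3. The window therefore runs at most 29 − 28 = 1 day past Visit 4. Visit 6 falls 28 + 14 = 42 to 42 + 21 = 63 days after Visit 4, and the Visit 4 window ends on Day 41. All three windows lie wholly inside the period.

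**Step 2. Nominal scored days per child.** These are simple sums. Consecutive 30-day windows overlap by at most 30 − 28 = 2 days when visits are at the minimum interval.

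| Endpoint | Coad and RTS,S | Control |
|---|---|---|
| Month 4.5, all-groups reading | 30 + 30 + 42 = 102 | 102 |
| Month 4.5, vaccine-dose reading | 102 | 42 |
| Whole study, as written | 30 + 30 + 42 + 30 = 132 | 42 + 4 × 30 = 162 |
| Whole study, Visits 2 and 3 added for Control | 132 | 162 + 60 = 222 |
| Generalized seizure, as written | 7 + 7 + 14 = 28 | 14 |

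**Step 3. Consequence of each reading.**

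- *All-groups reading at Month 4.5.* The whole-study endpoint drops 60 of the 102 Control days already scored (60/102 = 59%). A Control seizure after Visit 2 or 3 then counts at Month 4.5 but not over the whole study, so the cumulative count can be the smaller one.
- *Vaccine-dose reading at Month 4.5.* With equal background risk in every group, Coad and RTS,S would show 102/42 = 2.43 times the Control count from scored time alone.
- *Whole study.* The imbalance in days runs the other way: 162/132 = 1.23. Adding Visits 2 and 3 for Control gives 222/132 = 1.68. A single pooled total would therefore still not be comparable, and separate tabulation is needed.

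**Step 4. Size in events.** The documents give no background seizure rate. I assume 1 to 5 per 100 child-years, constant over time, with all 233 children followed.

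- 102 days: 233 × 102/365.25 = 65.1 child-years, or 0.65 to 3.25 expected Control seizures.
- 42 days: 233 × 42/365.25 = 26.8 child-years, or 0.27 to 1.34.

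The choice of reading moves the expected Control count by about 0.4 to 1.9 events.

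**The case against.** The best defence is that all three endpoints depend on vaccines or vaccine doses. Read literally, they agree that Control is not scored at Visits 2 and 3, and two of them say so by naming the groups. That is a fair reading of SAP 4.2 alone. It does not explain why Control's own schedule repeats the Visit 2 and 3 windows and marks recording from Visit 2. It also leaves the literal rule excluding the RTS,S-free background.

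Three stronger conclusions might be inferred, and the documents do not support them.

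- *That the endpoints flatly contradict each other.* The Month 4.5 endpoint is silent on groups. It does not state that Control is included.
- *That the comparator for doses 1 and 2 is lost.* Under the all-groups reading the Month 4.5 endpoint holds it in full. Under either reading, SAP 6.5.1 tabulates AEs of specific interest from Day 0, and SAEs within 30 days of every visit at which a product might be given. Protocol 8.1.2 cites convulsions without hospitalization as an example of a serious event. Such an event can appear if it was recorded.
- *That the wording biases the study against RTS,S throughout.* The 2.43-fold ratio needs the vaccine-dose reading and the shrinking cumulative count needs the all-groups reading, so both cannot apply at once. Over the whole study Control has more scored days, not fewer.

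It also stands that the stated safety objective compares Coad with RTS,S alone. Those groups have identical windows under every reading. SAP section 7 makes safety comparisons descriptive, so no success criterion changes.

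**Conclusion.** The inconsistency is real and remains in the current text of both documents. Control's scored time up to Month 4.5 is undefined between 102 and 42 days per child. Its whole-study seizure count need not contain its Month 4.5 count. Whole-study crude totals rest on 162 days against 132. For generalized seizures the as-written windows are 14 days against 28. The day counts rest on nominal windows, and the event range rests on the assumed background rate. The consequence is limited to the descriptive comparison with Control after RTS,S doses 1 and 2. With about 0.4 to 1.9 expected events at issue, one or two cases could change how that table reads. This is a low-cost improvement worth making, not a flaw that undermines the trial's main conclusions.

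**What to change.** 1. In SAP 4.2 and protocol 10.2, anchor the Visit 2, 3 and 4 windows on the visit, for all groups, in all three seizure endpoints. In the whole-study endpoint, then list the later visits by group (Visit 10 for Coad and RTS,S; Visits 6, 7, 8 and 12 for Control), so that the whole-study set contains the Month 4.5 set.
2. In SAP 6.5.1, tabulate seizures in the matched Visit 2 to 4 windows by group, separately from the later group-specific windows.
3. Reconcile protocol 8.2.1 (start of recording) and 8.1.5.2 (seizure definition) with Table 6 and its footnote d, so that Control recording runs from Visit 2.

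The cost is wording changes, one extra table, and a check that the seizure eCRF screens were completed for Control after Visits 2 and 3. Control's visits and its daily diary contacts for six days after each of those visits are already in the protocol, so no new contacts are needed. If the check finds screens missing, the report should say so and show what the SAE and unsolicited AE records hold.
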